#### **(ii) Phase 1 - VISIT 1 (Day 14) (After 14 days OF HANDIHALER TREATMENT)**

The patient attends the department.

- Patient to avoid short acting SABA and SAMA and LABA on day of visit
- 9am Baseline: Lung physiology measurements undertaken in this order; IOS, MBNW, Spirometry (FVC) /Body plethysmography (DLCO).
- Patient is trained for Respimat using Respimat demonstration device until observer satisfied.

- Patients switched to Respimat-Tiotropium 5 mcg od and instructed to take it at 10am every day. Patient takes first dose of Respimat-Tiotropium 5 mcg in the department during visit 1 at 10 am.
- 3 hours post dosing: Measurements IOS, MBNW, Spirometry/Body plethysmography undertaken 3 hours post-dosing

Tests:

- Small (IOS, MBNW, DLCO, FVC) airways (these will be done on physiology machines of [name])
- Large (FEV1, PEF) airways (these will be done on physiology machines of [name])
- CAT score

**AIM OF THIS PHASE (1) OF STUDY:** \*So here we want to see what is happening AFTER proper inhaler technique training on large and small airways lung function and also symptoms or exercise limitation (determined by CAT score)

### **(iii) Phase 2 - VISIT 2 (DAY 28 OF TIOTROPIUM TREATMENT)**

- Patient to avoid short acting SABA and SAMA and LABA on day of visit
- On Day 28 of -Tiotropium treatment patient attends lab and performs the following tests at 9am: IOS, MBNW, Spirometry/Body plethysmography.
- Measurements IOS, MBNW, Spirometry/Body plethysmography undertaken at 10 am.

**AIM OF THIS PHASE (2) OF STUDY:** \*So here we want to see what is happening AFTER this efficient device Respimat (trained) compared to PREVIOUS device Handihaler (trained) on large and small airways lung function and also symptoms or exercise limitation (determined by CAT score). Here we want to see if the properties of the Respimat device with deeper lung deposition (slow velocity and small particles) can improve small airway measures (and indeed large airway measures) that might also be related to an improvement in symptoms.

## **5. PATIENT ELIGIBILITY**

Patients will be eligible for the study if they have COPD and satisfy the following criteria:

### **Inclusion Criteria**

- 1) Patients with FEV1/FVC <70% predicted.
- 2) Mild (GOLD stage I: FEV1 >80% pred.) to moderate (GOLD stage II: FEV1 50-80% pred.)
- 3) Aged 30 years onwards – there is no upper age limit as we do not want to exclude elderly patients as COPD is primarily a disease in the elderly population.
- 4) Have ongoing symptoms or exercise limitation (determined by CAT score)

- 5) Stable COPD (no chest infection requiring antibiotics and/or oral steroids in the past 2 months).
- 6) Capable of giving informed consent, which includes compliance with the requirements and restrictions listed in the consent form.

### **Exclusion Criteria**

- 1) We will not recruit subjects who lack the capacity to consent.
- 2) Current or past diagnosis of asthma.
- 3) Patients on concurrent oral bronchodilators (theophylline, PDE4 inhibitors) will not be included.
- 4) Patients on other LAMAs will not be included
- 5) History of any chronic respiratory diseases other than COPD.
- 6) History of another medical condition, which in the opinion of the Unit Physician, contraindicates his/her participation in the study.
- 7) Clinical evidence of heart failure (NYHA class III-IV).
- 8) Unstable respiratory disease in the last four weeks prior to the screening visit (indicated by any change in their maintenance inhaled therapy or who have had a lower respiratory tract infection in the previous four weeks).
- 9) Evidence of a respiratory exacerbation requiring emergency room treatment and/or hospitalisation within four weeks before screening.
- 10) Use of systemic (oral or intravenous) steroids 4 weeks prior to inclusion (injectable depot steroids 6 weeks) or more than 3 periods during the last 12 months.
- 11) Participants with a known or suspected allergy, sensitivity or intolerance to the study drugs (this will be asked directly at the screening visit) or patients with a history of another drug allergy which, in the opinion of the Unit Physician, contraindicates his/her participation in the study.
- 12) Patients with known or suspected cardiac rhythm disorders
- 13) Patients treated with beta-blockers in the week preceding the screening visit and during the study period.
- 14) Females who are pregnant or lactating or are likely to become pregnant during the trial. Women of childbearing potential may be included in the study if, in the opinion of the investigator, they are taking adequate contraceptive precautions.
- 15) Patients who have evidence of alcohol or substance abuse.
- 16) Participation in another clinical trial with an investigational drug in the four weeks preceding the screening visit.

17) Contraindication to taking Tiotropium bromide

## **6. CONCOMITANT THERAPIES**

Patients on other LAMAs including oral bronchodilators (theophylline, PDE4 inhibitors) are excluded from the trial. Patients on concurrent LABAs will be allowed.

## **7. STUDY TESTS**

- Small (IOS, MBNW, DLCO, FVC) airways (these will be done on the physiology machines of [name])
- Large (FEV1, PEF) airways (these will be done on the physiology machines of [name])
- CAT score

## **8. DRUG DOSING**

The study drugs, Handihaler tiotropium 18 micrograms and Respimat tiotropium 5 micrograms and the placebo, for training purposes, will be supplied by Boehringer Ingelheim (Germany) to the Pharmacy of the Royal Brompton Hospital where it will be stored until required. Labels will be assigned to study medication and placebo in accordance to the protocol and ICH GCP by the Pharmacy of the Royal Brompton Hospital – as final packaged medication for each patient. The labels on the packages and unit medication will specify all necessary information for a correct identification of the medication boxes and individual medication units. The Pharmacy of the Royal Brompton Hospital will dispense the study drugs to the patients. All study medication accountability will be performed at the Royal Brompton Hospital by members of the study team and returned/unused medication will be destroyed by the Royal Brompton Hospital Pharmacy at study closure.

We will give 14 days duration of treatment in order to achieve steady state dosing of Tiotropium drug.

- The first dose will be given in the Hospital but subsequent doses will be taken at home.
- Dosing of the drug will be undertaken at the same time each day (ideally 9am)
- We will undertake measurements 3 hours post dosing (applies only to the dose given in the department). The reason we have used 3 hours is to achieve the maximal response pharmacologically with Tiotropium in order to elicit differences within Phase 1 of the study (device training ) and Phase 2 (device effects) in Study Group 1.
- We will use Handihaler tiotropium 18 micrograms daily which is licensed for use in COPD.
- We will use Respimat tiotropium 5 micrograms daily which is licensed for use in COPD.

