#### **WHAT HAPPENS AT EACH VISIT?**

##### **(i) Phase 0 - SCREENING VISIT: (DAY 0)**

- IDENTIFY : Mild-moderate COPD [G.O.L.D], established (>1 month) already on HandiHaler- Tiotropium 18 mcg once daily but have ongoing symptoms or exercise limitation (determined by CAT score) to be eligible to enter
- Patient to avoid short acting SABA and SAMA and LABA on day of visit

- 9am Baseline: Lung physiology measurements undertaken in this order; IOS, MBNW, Spirometry (FVC) /Body plethysmography (DLCO).
- Patient asked to demonstrate how they use Handihaler with a demonstration device. Research observer notes how patient takes Handihaler-Tiotropium to assess good or poor inhalation technique /errors.
- Patient receives training in how to use Handihaler correctly until observer satisfied.
- 10am Patient takes Handihaler-Tiotropium 18 mcg od in Lab. Research observer notes how patient takes Handihaler-Tiotropium.
- 3hours post dosing: Lung physiology measurements undertaken in this order; IOS, MBNW, Spirometry (FVC) /Body plethysmography (DLCO).

Tests:

- Small (IOS, MBNW, DLCO, FVC) airways (these will be done on physiology machines of [name])
- Large (FEV1, PEF) airways (these will be done on physiology machines of [name])
- CAT score

**AIM OF THIS PHASE (0) OF STUDY:** Here we want to see that if patients have ongoing symptoms but are on Handihaler-Tiotropium what is happening PRIOR to proper inhaler technique training – that is their ‘real-life’ use of the inhaler - to their lung function (large and small airways) and also symptoms or exercise limitation (determined by CAT score) will already be recorded as entry criteria

- Patient will be asked to take Handihaler-Tiotropium 18 mcg od at 10am every day for 14 days

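### Section 8 assigns the 3-hour tests to the training and device effects, but neither planned contrast can be formed at 3 hours, and the readable text does not say which reading or which 14-day contrast is primary for R5-R20

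*Protocol*

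**What the plan says.** **Purpose of the 3-hour tests (Protocol section 8).** "The reason we have used 3 hours is to achieve the maximal response pharmacologically with Tiotropium in order to elicit differences within Phase 1". The sentence then adds Phase 2 and labels the two phases as training and device effects. The same section limits these tests: "We will undertake measurements 3 hours post dosing (applies only to the dose given in the department"). It also says: "The first dose will be given in the Hospital but subsequent doses will be taken at home". The treatment length has a separate reason: "We will give 14 days duration of treatment in order to achieve steady state dosing of Tiotropium drug".

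**Contrasts (Protocol section 2).** Phase 1 sets Visit 1 against Screening. Phase 2 sets Visit 2 against Visit 1.

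**Visit schedule (Protocol section 4).**
- Screening: "9am Baseline: Lung physiology measurements undertaken in this order; IOS, MBNW, Spirometry (FVC) /Body plethysmography (DLCO"). Then "Patient receives training in how to use Handihaler correctly until observer satisfied", a HandiHaler dose at 10am, and a second set of tests 3 hours later.
- Visit 1 (Day 14): 9am tests, again labelled as baseline, then Respimat training, the first Respimat dose at 10am, and tests 3 hours later.
- Visit 2 (Day 28): tests at 9am and at 10am. No department dose and no 3-hour test is listed.

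**Primary endpoint (Protocol section 10 and SAP).** R5-R20, with an assumed change from baseline to 14 days of 0.03 kPa/(L/s), SD 0.05, and N = 44. The SAP's analysis sentence names no visit and no reading.

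**Clock times.** Section 8 has "Dosing of the drug will be undertaken at the same time each day (ideally 9am"), while section 4 has 10am. The visit-day restriction is "Patient to avoid short acting SABA and SAMA and LABA on day of visit"; it does not mention tiotropium.

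**The concern.** R5-R20 and the lung-function secondary endpoints are measured twice at every visit. Only one sentence links a test time to the phase effects, and it points to the 3-hour data.

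Visit 1 serves both contrasts, yet its two readings belong to different devices. If the 3-hour reading were used, Phase 1 would credit a Respimat dose to HandiHaler training. In Phase 2, the HandiHaler reference would contain a Respimat dose, read at what section 8 regards as peak effect.

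Section 10 and the SAP do not settle the matter. They name the day but not the reading, and both the Screening-to-Visit 1 and the Visit 1-to-Visit 2 intervals last 14 days.

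**Working it through.** **1. The plan's own figure.** For a paired difference, n = ((z₀.₉₉₅ + z₀.₉₀) × SD / δ)². With SD = 0.05 and δ = 0.03 this is ((2.576 + 1.282) × 0.05 / 0.03)² = 41.3, so 42. The exact paired t calculation gives 45, with power 0.894 at N = 44 (two-sided 1%). The stated 44 is therefore reproduced within rounding and method. What is missing is which reading and which contrast the 0.03 and 0.05 describe. The SD matters: if that of the chosen contrast were 0.04, 0.06 or 0.07 (assumed range), power at N = 44 would be 0.986, 0.730 or 0.562.

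**2. State at each test (Protocol section 4).**

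| Visit | 9am test | 3-hour test |
|---|---|---|
| Screening | HandiHaler as used at home, before training | First HandiHaler dose after training |
| Visit 1 | 14 days of trained HandiHaler | First Respimat dose |
| Visit 2 | 14 days of Respimat | None listed (second set is at 10am) |

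**3. Contrasts available, as section 2 defines them.**

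| Contrast | States needed | At 9am | At 3 hours |
|---|---|---|---|
| Phase 1: Visit 1 − Screening | Trained v. untrained HandiHaler | Yes | No: first Respimat dose v. first trained HandiHaler dose |
| Phase 2: Visit 2 − Visit 1 | Respimat v. trained HandiHaler | Yes | No: no Visit 2 value, and Visit 1 is already Respimat |

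Result: 2 of 2 at 9am and 0 of 2 at 3 hours.

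**4. Cross-check on doses.** The synopsis (maximum dosage item) counts 14 doses per device: 14 × 18 = 252 and 14 × 5 = 70 micrograms. HandiHaler doses on Days 0 to 13 and Respimat doses on Days 14 to 27 leave no HandiHaler dose for Visit 1 and no Respimat dose for Day 28.

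**5. Within-visit reading (3-hour minus 9am).** Training cannot be isolated, because no untrained dose is followed by a test. Comparing the Screening and Visit 1 responses sets one HandiHaler dose, after untrained home use, against one Respimat dose, after 14 days of trained HandiHaler. That is not the 14-day device effect.

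**6. Time since the last dose at the 9am tests.** With 10am dosing, 10am Day 13 to 9am Day 14 is 23 h, and 10am Day 27 to 9am Day 28 is 23 h. With 9am dosing the day before, both are 24 h. Before Screening the interval is not fixed, because the 10am instruction starts at that visit. As an assumption for illustration, once-daily home dosing at 10am the day before gives 23 h (gap to Visit 1: 23 − 23 = 0 h), and at 9pm the evening before gives 12 h (gap: 23 − 12 = 11 h). The documents give no acute effect on R5-R20, so these hours cannot be turned into a bias.

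**The case against.** **The plan does name a time.** A reader might infer that R5-R20 has no analysis time point at all. The documents do not support that: section 10 and the SAP give baseline and 14 days. Section 4 attaches the baseline label only to 9am tests, and the 14-day course is justified by steady state. All this favours 9am. It stops short of settling it, because the label occurs at two visits and not at Visit 2, and the 14-day change is not tied to it.

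**Section 8 may not mean the section 2 pairs.** It speaks of differences within phases. Screening against Visit 1 at 3 hours compares the first supervised doses of the two devices at the same time after dosing, so it has some bearing on device at peak. That stands, but the comparison is confounded by period and by 14 days of trained HandiHaler use, and is neither planned contrast.

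**Unseen material.** The section 10 figure and the section 11 flow-chart are not shown and may name a reading. They could not rescue the 3-hour contrasts against the visit text. A 3-hour test at Visit 2 would give Respimat against Respimat and would conflict with section 8's own limit to the hospital dose. Nor could they supply an untrained dose at Screening.

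**The sentence may be a remnant.** It refers to a Study Group 1 that the readable text defines nowhere else. That is a plausible inference, and a further reason to correct it.

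**Conclusion.** The point holds. Under the visit text, the 3-hour tests cannot show either phase effect as section 2 defines it (0 of 2), while the scheduled 9am tests match the device and training state for both (2 of 2). The readable text leaves open whether the 14-day R5-R20 change uses the 9am or the 3-hour reading, and which 14-day contrast is primary.

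Three stronger conclusions should not be drawn:
- That the trial cannot address its questions: the 9am tests supply both before-and-after contrasts.
- That N = 44 is wrong: it reproduces.
- That a mismatch in time since dose of most of a day exists at Screening: once-daily use with that day's dose taken in the laboratory at 10am does not imply a home dose the same morning, and no bias can be sized.

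Harm arises only if the choice is left open or follows section 8. The point should be fixed before analysis. It rests on the section 4 text being the operative schedule. Confidence is moderate because of the two figures not shown.

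**What to change.** - In Protocol sections 2, 8 and 10 and the SAP, state that for R5-R20 and all lung-function secondary endpoints the Phase 1 contrast is Visit 1 9am minus Screening 9am, and the Phase 2 contrast is Visit 2 9am minus Visit 1 9am.
- State which of the two is the primary R5-R20 contrast to which the 0.03 and 0.05 refer, and whether those figures are for 9am values.
- Report the Screening and Visit 1 3-hour data as exploratory acute response only, and remove the section 8 claim that they show the phase differences.
- Record the time of the last tiotropium dose at each visit, including Screening, and report it beside each contrast.
- Reconcile the dosing times (9am in section 8, 10am in section 4) and the two Visit 2 test times before calling the 9am tests pre-dose.
- If the section 10 figure or the flow-chart already names the reading, carry it into the protocol text and the SAP.

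Cost: wording changes and one recorded time per visit, with no new visit or test. The trial gives up a peak-effect claim for either phase, although section 8 shows an interest in one. If the 0.03 and 0.05 came from post-dose data, the sample size must be rechecked.

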## **9. DRUG SUPPLY AND MANAGEMENT**

- Drugs will be bought from the Royal Brompton Hospital Pharmacy (Where it has been delivered to by Boehringer Ingelheim ).
- Placebos for training will be supplied by Boehringer Ingelheim.

## **10 . SAMPLE SIZE CALCULATION: PRIMARY ENDPOINT / SECONDARY ENDPOINTS**

[figure not shown]
**The primary endpoint is the Impulse oscillometry measure of IOS R5-R20.**

**Each subject will act as their own control and assuming the treatment effect (ie the difference R5-R20 between baseline and 14 days) to be 0.03kPa(L/s) with an SD of 0.05, then 44 subjects will be required to achieve the treatment effect at 1% significance and 90% power.**

**ANALYSIS:**

**The secondary endpoints are** small airways (MBNW, DLCO, FVC) and large airways (FEV1, PEF) airways physiology and also the CAT score.

## **11. STUDY TREATMENT DOSING FLOW-CHART**

## **12. INFORMED CONSENT**

Patients will be recruited by a member of [name] team at the Royal Brompton. At this point they will receive an information sheet and an appointment will be made for them with the research nurse to discuss enrolment into the study. All participants will provide written informed consent. The Informed Consent Form will be signed and dated by the participant before entering the study. The Investigator will explain the details of the study and again provide a Participant Information Sheet, ensuring that the participant has sufficient time to consider participating or not. The Investigator will answer any questions that the participant has concerning study participation.

Each participant has the right to withdraw from the trial at any time. In addition, the investigator may discontinue a participant from the trial at any time if the investigator considers it necessary for any reason e.g. pregnancy, ineligibility

## **13. TREATMENT DISCONTINUATION CRITERIA**

A patient that experiences any serious adverse event (SAE), intolerable adverse event (AE), or becomes pregnant must have treatment withdrawn. Patients who fail eligibility criteria must be withdrawn from the trial

## **14. DEFINITION OF END OF TRIAL**

The last visit of the last subject

## **15. SAFETY AND ETHICAL CONSIDERATIONS:**

### ***Safety of Procedures & Intervention:***

i) **Lung Function** is performed in a safe environment in the RBH Respiratory BRU CRF. Some participants may experience transient coughing after performing a forced blowing manoeuvre into the machine, but this is often short lived and self-rectifying.

ii) **Impulse Oscillometry (IOS)** is performed in a safe environment in the RBH Respiratory BRU CRF. There are no potential adverse effects associated with IOS.

iii) **Multi-Breath Washout Test (MBW)** is performed in a safe environment in the RBH Respiratory BRU CRF. Participants may experience a slight dryness in their mouth from the breathing test which takes approximately 5 minutes. Water will be provided for patients and they will be seated on a comfortable chair.

### ***iv) Tiotropium Bromide***

Any patient with a contraindication to taking Tiotropium bromide, listed in the British National Formulary (BNF) will not be entered into this study. This will form part of the exclusion criteria.

### ***v) Foreseeable A serious adverse event (SAE) for Tiotropium as listed in BNF.***

Taste disturbance, stomatitis, gastro-oesophageal reflux, epistaxis, oropharyngeal candidiasis, intestinal obstruction (including paralytic ileus) laryngitis, insomnia, urinary-tract infection, skin infection, sinusitis, dental caries, gingivitis, glossitis, skin ulcer, joint swelling, dry skin. These will not be reported as SAE but will be logged appropriately.

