### ***Adverse events***

An **adverse event** (AE) is the development of an undesirable medical condition or the deterioration of a pre-existing medical condition following or during exposure to a pharmaceutical product, whether or not

considered causally related to the product. An undesirable medical condition can be symptoms (e.g., nausea, chest pain), signs (e.g., tachycardia, enlarged liver) or the abnormal results of an investigation (e.g., laboratory findings). In clinical studies, an AE can include an undesirable medical condition occurring at any time, including run-in or wash-out periods, even if no study treatment has been administered.

A **serious adverse event (SAE)** is an AE occurring during any study period (i.e., run-in, treatment, wash-out, follow-up), and at any dose of the investigational product, comparator or placebo, that fulfils one or more of the following criteria:

- results in death
- is immediately life-threatening
- requires in-patient hospitalisation or prolongation of existing hospitalisation
- results in persistent or significant disability or incapacity
- is a congenital anomaly or birth defect
- is an important medical event that may jeopardise the patient or may require medical intervention to prevent one of the outcomes listed above

A distinction should be drawn between serious and severe events. A severe event is a major event of its type. The term “severe” is used to indicate the intensity of a specific event, while the term “serious” is based on patient/event outcome or action criteria.

A **suspected unexpected serious adverse reaction (SUSAR)** is any adverse event with a reasonable possibility of a link to the study drug that is both serious and unexpected (i.e. not consistent with the information about the study drug in either the SPC or IB).

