### **Procedures for Serious Adverse Event Reporting**

An SAE form should be completed and faxed to the Trial Manager/Chief Investigator for all SAEs (or AESIs) within 24 hours. The Trial Manager/Chief Investigator should inform the sponsor of all SAEs within 24 hours of receiving notice. All SAEs should be recorded on the annual safety reports that are sent to the MHRA and REC on the anniversary of the date a favourable opinion for the study was given.

Contact details for reporting SAEs and SUSARs [contact], attention [name] Please send SAE forms to: [name] [contact] (Mon to Fri 09.00 – 17.00)

Contact details for reporting SAEs and SUSARs to the Sponsor [contact]

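### Protocol section 15(v) takes 17 listed event types out of SAE reporting whether or not they are serious, which conflicts with the rules that require every SAE to be reported

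*Protocol*

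**What the plan says.** Three parts of protocol section 15 bear on this point.

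- **Section 15(v).** The heading labels the events as foreseeable serious adverse events of tiotropium, taken from the BNF. A list follows, running from taste disturbance to dry skin and including intestinal obstruction, urinary-tract infection, skin infection and epistaxis. It closes: "These will not be reported as SAE but will be logged appropriately". How the events are to be logged is not explained.
- **Adverse events.** An SAE is an adverse event "that fulfils one or more of the following criteria". There are six criteria; one is that the event "requires in-patient hospitalisation or prolongation of existing hospitalisation". The section adds that the term serious "is based on patient/event outcome or action criteria".
- **Procedures for Serious Adverse Event Reporting.** "An SAE form should be completed and faxed to the Trial Manager/Chief Investigator for all SAEs", within 24 hours. The Trial Manager or Chief Investigator "should inform the sponsor of all SAEs within 24 hours of receiving notice". Finally, "All SAEs should be recorded on the annual safety reports that are sent to the MHRA and REC".

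The SAP does not deal with safety reporting.

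**The concern.** Section 15(v) decides by the name of the event. The SAE definition and the reporting procedures decide by what happened to the patient. The two tests give different answers whenever a listed event turns out to be serious, and the protocol does not say which one governs.

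What is at stake is whether safety reporting is complete and consistent. A site that relies on 15(v) could leave a serious event without an SAE form and without notice to the sponsor, and the event might also be missing from the annual report to the MHRA and REC. Another site member, relying on the reporting procedures, would report the same event in full. The event would be logged in either case, and no efficacy endpoint or its analysis is touched.

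**Working it through.** The plan states no figure on this point to reproduce. The check is a count, a comparison of the texts, and a ceiling on exposure.

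**1. Count of listed event types (section 15(v)).** As printed there are 16 comma-separated items. A comma is missing between intestinal obstruction (with paralytic ileus) and laryngitis, which are separate conditions, so the count is 16 + 1 = 17. The number carrying a condition on seriousness, hospitalisation or outcome is 0.

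**2. Exceptions elsewhere.** The SAE definition has 6 criteria: death, immediate threat to life, hospital admission or a longer stay, disability, congenital anomaly, and important medical event. It has 0 exceptions for listed or expected events. The reporting procedures contain 3 steps, each applied to all SAEs, and also have 0 exceptions. Neither section refers back to the list.

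**3. One case taken through the text.** Suppose a patient is admitted to hospital with intestinal obstruction during treatment.

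- Adverse events section: the admission meets a criterion, so the event is an SAE.
- Reporting procedures: it is an SAE, so the form, the sponsor notice and the annual report entry are all required.
- Section 15(v): it is a listed event, so it is not reported as an SAE.

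The second and third instructions cannot both be followed.

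**4. Steps that could be missed.** Two are directly affected by the exemption: the 24-hour form and the sponsor notice. A third, the annual report entry, depends on what the logging is meant to include. That makes up to 2 + 1 = 3. The copy to the sponsor's representative, required under SUSAR and SAE reporting, is taken here to follow from an SAE report being made and is not counted separately.

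**5. Exposure ceiling.** Inputs are the maximum of 44 patients (synopsis item 8) and the maximum treatment duration of 28 days (synopsis item 15).

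- 44 × 28 = 1,232 patient-days
- 1,232 / 365.25 = 3.37 patient-years

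The documents give no rate for any listed event, so an expected number of affected events cannot be calculated.

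**The case against.** The strongest reply is that 15(v) is a deliberate, specific exemption for foreseeable events, placed just ahead of the general rules, and that specific text normally qualifies general text. The heading supports this, since it calls the events SAEs. On that reading the fault is only a missing cross-reference. But the exemption is not carried into the reporting procedures, which refer to all SAEs at each of three steps, so the contradiction stands until it is written there.

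A second reply is that 15(v) means only non-serious occurrences. The text does not say so, the heading points the other way, and the sentence would then be unnecessary, because non-serious events are already outside SAE reporting.

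A third is that expedited SUSAR reporting remains open. That is correct, and expectedness there is judged against the SPC or IB rather than the BNF list. But a SUSAR must be both serious and unexpected, so this route is not designed to catch serious events that are foreseeable.

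Some points on size do stand. The conflict arises only when a listed event meets a criterion, so 17 is the width of the exemption and not a count of 17 separate problems; several listed types, such as dry skin, would seldom matter. Patients have already been on HandiHaler tiotropium for more than a month, and those with known intolerance or a contraindication are excluded. Synopsis item 11 points to both the safety and adverse-event sections without ranking them, but it concerns symptom questioning at visits and adds little. These points limit the reach and leave the conflict in place.

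**Conclusion.** The concern holds. For any listed event that meets a seriousness criterion, section 15(v) and the SAE reporting procedures give opposite instructions, and nothing in the protocol settles which prevails. The exemption covers 17 event types without any seriousness condition; two reporting steps are directly at risk and a third possibly.

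The practical reach is small, at most about 3.4 patient-years of treatment, and no endpoint result depends on it. The point should still be corrected, because a reporting instruction has to work for the first case that arises.

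The conclusion rests on the wording alone. What the authors intended by the exemption, and whether each listed event is expected under the SPC or IB, cannot be determined from the documents.

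**What to change.** Reconcile section 15(v) with the SAE definition and the reporting procedures. Either delete the sentence that removes the listed events from SAE reporting, or limit it, for example:

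> Listed events that meet none of the seriousness criteria in the Adverse events section will be logged as AEs. Any listed event that meets a criterion will be reported as an SAE under Procedures for Serious Adverse Event Reporting.

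If the sponsor does intend an exemption for some serious listed events, it should justify it, state its scope, write it into the reporting procedures, and say whether such events still enter the annual safety report. The same edit should restore the missing comma before laryngitis and correct the garbled heading of 15(v).

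Section 13 makes treatment withdrawal depend on any SAE. Section 15(v) concerns reporting and does not necessarily change an event's SAE status, but section 13 should be read in the same reconciliation so that the term is used consistently.

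The cost is about one sentence of protocol text and possibly a few more SAE forms.
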